**1. FUNDING INFORMATION**

1.1 Is your study funded (either directly or through a sub-award) by a Federal Agency (i.e., HHS, NIH, NSF, DOD, DOE, DOJ, or EPA, etc.)?

Yes  
 No

1.2 Is your study funded (or will it be) by the National Institutes of Health (NIH)?

Yes  
 No (***please go to next section***)

1.3 Does your study meet the definition of a “**Clinical Trial**”?

Yes  
 No

HHS and NIH define a **clinical trial** as “a research study in which one or more human subjects are prospectively assigned to one or more interventions (which may include placebo or other control) to evaluate the effects of the interventions on biomedical or behavioral health-related outcomes.”

If your study meets the definition of a **clinical trial**, there are additional requirements that you must follow. Ask your assigned IRB Reviewer or see the [HUA IRB website](#) for more information.

**2. RESEARCH COLLABORATIONS AND LOCATIONS**

## LOCATIONS

*Locations refer to the geographic location where the research will take place, not to the people or institutions that you may be collaborating with. Knowing the location helps the IRB determine the local context of the research as well as if there are additional laws, regulations, and policies researchers need to adhere to. If conducting online studies, please indicate the location of the researcher who is hosting.*

2.1 Where will this study take place?

- Harvard University
- At another location in Massachusetts
- In another US state (*see below*)
- Internationally (*see below*)

*If you chose “in another US state” or “Internationally” describe the laws that will need to be considered:*

The proposed study will be conducted online. As such, persons from internet access can participate in the study.

***Please ensure that what you have marked above matches what has been indicated in the ESTR SmartForm, section “Research Locations.”***

2.2 Do you plan to obtain data from individuals located in the European Economic Area (EEA)\*?

- Yes – Please go to next question
- No – Skip to #2.4

*If “YES” the data you obtain may be subject to the E.U. General Data Protection Regulation (GDPR). Click [here](#) for more information.*

*\* The EEA includes the 28 states of the European Union and four additional countries: Iceland, Liechtenstein, Norway, and Switzerland. Note that this regulation may also apply to data obtained over the internet.*

2.3 Will data collected from individuals located in the EEA include any of the following? (mark all that apply)

- Racial or Ethnic Origin
- Political Opinions
- Religious or Philosophical Beliefs
- Trade Union Membership
- Sexual Orientation
- Data concerning a person’s sex life
- Biometric Data
- Genetic Data

2.4 Are there any U.S. state laws, international laws, or other laws that the IRB will need to consider when reviewing this study?

- Yes (*see below*)
- No

**If "Yes" describe the laws that will need to be considered:**

2.5 Thinking about the locations where this study will take place, are there any permissions that must be obtained from cooperating institutions, community leaders, government officials? *This may include a review by a local ethics board, school district, Ministry of Health, or other institutional approval process, whether domestic or international. A statement that formal review is not required along with your source of information that the proposed research is in accordance with local laws, regulations, and customs is also acceptable.*

Yes (see below)

No

**If "Yes" describe and if available, upload any permission documents to the ESTR SmartForm section "Local Site Documents."**

2.6 Are there any community or cultural differences for the local population of participants that require consideration? *For example, cultural or gender dynamics or social structure considerations.*

Yes (see below)

No

**If "Yes" describe:**

## COLLABORATIONS/SITES

*Collaborations, known as "sites" in ESTR, refer to people or institutions that are also taking part in the research study. An important part of knowing about these collaborations is knowing what each person/institution is doing in the research in order to determine the scope of IRB review.*

2.7 Will you be collaborating with any researchers not affiliated with Harvard University Area to carry out this study? *HMS, HSPH, and HSDM are not part of Harvard University Area.*

Yes

No (skip to next section)

2.8 Will the actions of these collaborators include any of the following: Have contact with human subjects; Have access to data that is identifiable; OR Are responsible for the design, conduct, or reporting of the research?

Yes

No (skip to next section)

2.9 Will these collaborators receive their own IRB review?

Yes, all will receive their own IRB review (skip to next section)

No, none will receive their own IRB review

Some will receive their own IRB review and some will not

2.10 Is another institution and/or researcher requesting that the Harvard University Area IRB act as the IRB of record ("Reviewing IRB") for that institution's or that researcher's activities on the study?

Yes

No (see below)

We are working with staff members at The Mighty who have agreed to implement the study. At no point will they send us data that may compromise the identity of the research participants. The technology team at TheMighty will manage the platform, administer the surveys, and store the data. They have had extensive experience in surveying their users prior to this research project.

3.3 Are there any other additional study staff whose role in this study requires special qualifications in addition to ethics training (e.g., licensed clinical psychologist, phlebotomist, etc.)?

Yes (see below)

No

*If "Yes" describe:*

#### 4. RESEARCH PURPOSE

4.1 Provide a brief, non-technical description of the purpose of the research, including the research questions that you hope to answer.

Suicide is a leading cause of death in the US, and rates have been increasing in recent years. Despite a preponderance of research, few effective interventions exist to curb suicidal thoughts and behaviors (STBs). These interventions tend to be expensive, suffer from low engagement, or pose difficulties to

scale on a population level. Could a highly engaging modality such as social media be designed to decrease STBs?

Social media platforms produce highly engaging materials that can be disseminated quickly and freely to millions. Furthermore, the materials on these websites are produced by patients themselves, which may serve to increase acceptability among those at high risk for STBs. Lastly, these platforms are capable of monitoring data about its users as well as surveying users about their past or current STBs, thereby allowing for rigorous analysis of these thoughts and behaviors. We propose to curate a curriculum consisting of articles which have individually been shown to decrease suicidal ideation (SI) on a social media platform, and to test whether administering this reading curriculum can decrease STBs.

4.2 Describe the scientific background, rationale for the study, and importance of this research in adding to existing knowledge.

Suicide rates have increased in nearly every state over the past decades (CDC, 2018). Currently, there is no effective, widely-used, and economically viable solution to decrease STBs. Some promising work suggests that brief interventions such as sending care letters or text messages to recently discharged inpatients may decrease STBs (Motto et al., 2001, Comtois et al., 2019). Clinical treatment consisting of assigning readings—so-called bibliotherapy—have been demonstrated to decrease depressive symptoms, although not suicidality (Gualano et al., 2017). Other researchers have designed a smartphone-based video game that can reduce STBs in the short term (Franklin et al., 2016). However, the overall effect sizes of these interventions are generally small, the level of patient engagement tends to be low, and these proposed solutions are difficult to implement at scale. Social media platforms have been able to create high engagement by aggregating user-generated materials. Can such a platform be helpful in improving mood and reducing STBs?

TheMighty.com is an online social network that was designed to create online communities for patients who are dealing with healthcare challenges. Many of the user-generated articles on suicide have been viewed hundreds of thousands of times by others. Through surveys and usage patterns, The Mighty has a detailed understanding on how these materials are affecting their users. By reviewing preliminary internal survey data, we plan to help The Mighty curate a list of articles which are correlated with decreased suicidality after users read them. After identifying a set of articles associated with decreased STBs in the short-term, we hypothesize that providing users with a daily curriculum of these helpful articles over the course two weeks may be beneficial to them. We plan to work together with team members at The Mighty to investigate whether administering such a curriculum can decrease STBs, and if so, how long these effect would last. In order to investigate this question, we propose to conduct a randomized controlled trial in which new online users are either randomized to the suicide prevention curriculum with daily surveys, or to a control condition in which users will receive only the same surveys with no suicide prevention curriculum.

If we are successful, we will have designed the first social media-generated intervention that decreases suicidal thoughts and behaviors. The success of this study will have significant clinical implications: clinicians can easily refer patients to subscribe to accessible, effective, and free interventions online.

References:

Comtois, Katherine Anne, Amanda H. Kerbrat, Christopher R. DeCou, David C. Atkins, Justine J. Majeres, Justin C. Baker, and Richard K. Ries. "Effect of Augmenting Standard Care for Military Personnel With Brief Caring Text Messages for Suicide Prevention: A Randomized Clinical Trial." *JAMA Psychiatry*, February 13, 2019. <https://doi.org/10.1001/jamapsychiatry.2018.4530>.

Franklin, Joseph C., Kathryn R. Fox, Christopher R. Franklin, Evan M. Kleiman, Jessica D. Ribeiro, Adam C. Jaroszewski, Jill M. Hooley, and Matthew K. Nock. "A Brief Mobile App Reduces Nonsuicidal and Suicidal Self-Injury: Evidence from Three Randomized Controlled Trials." *Journal of Consulting and Clinical Psychology* 84, no. 6 (June 2016): 544–57. <https://doi.org/10.1037/ccp0000093>.

## 5. STUDY PROCEDURES

### 5.1 Provide a complete overview of the study:

- Describe the procedures participants will be asked to complete or undergo.
- Explain step by step what participants will be asked to do
- Include how long the procedures will take.

***If your study includes multiple variations of the procedures, please make clear which procedures are included in the variations.***

This study is a randomized controlled trial (RCT) design, in which consenting participants who are 18 or older will be randomized to two conditions: Active Treatment (AT) and Control.

Study Overview: Participants in the AT condition will be assigned to read one story from the mighty per day and to complete a brief online survey. Participants in the Control condition will first be assigned to complete surveys only, but then will receive the same one-story-per-day intervention as the AT condition.

Story selection procedure: We will identify a set of 40-50 already-published stories on TheMighty that are most likely to help individuals thinking about suicide to feel (A) more optimistic about the future and (B) more connected to other people. In order to identify these articles, will use insights from the team at TheMighty as well as qualitative analysis of the content of published stories.

#### Part 1: Feasibility Trial

In order to ascertain the most appropriate parameters for the clinical trial, a feasibility trial will be run initially with 50 participants. Each of these first 50 participants will be entered into the raffle, regardless of whether they completed 75% of daily surveys.

When potential subjects click on articles relating to suicide, a pop-up asks patients whether they would like to participate in a study. If the user answers in the affirmative, a short questionnaire will screen in the appropriate subjects.

AT Condition: Participants in the AT condition will be provided at least 1 article per day during the 5-to-14-day initial study period by The Mighty platform management team. The articles provided in the AT

[figure not shown]
Condition will come from a predefined set of articles. This set of articles was chosen based on preliminary research by The Mighty platform management team suggesting that reading these articles was associated with a reduction in negative mood and/or self-injurious thoughts. The specific AT Condition articles will be provided before participants are recruited. Note: The articles in this condition are publicly posted articles/blog posts written by visitors to TheMighty.com. For a sample of articles see here: <https://themighty.com/topic/suicide/>. Participants in the AT condition will also receive a survey before and after each article. This survey will contain items assessing the following constructs: optimism, social connectedness, identification with the story's author, and suicidal ideation.

Control Condition: Participants in the Control condition will be sent emails with the same survey as those in the AT condition, but they will not receive articles.

After the feasibility trial is conducted, we will adjust the parameters of the research protocol such as length, timing for sending email, number of articles sent, etc. For example, it is plausible that most participants stop engaging after 5 days. If this is the case, the length of the study may be decreased from 14 days to as few as 5 days.

Part 2: Research Trial (See diagram below for timeline)

The protocol for the actual research trial is nearly identical to the feasibility trial described above. We will recruit 500 patients total during the research trial. Patients will be randomized to either the AT or Control condition, with approximately 50% of the sample in each condition. Based on the results of the feasibility trial, we may adjust parameters in order to maximize meaningful engagement. Such parameters may include the number of articles sent, frequency of sending articles, timing of when articles are sent, etc. Additionally, all patients will receive a follow-up survey at 2 weeks after the 5-14 day intervention period in order to assess whether the effect of reading articles is sustained. These follow-up surveys will assess similar constructs to those assessed at baseline and during the intervention period. One week following administration of the follow-up surveys, participants in the Control condition will receive the same intervention (1 article assigned per day with pre- and post-article surveys) as those in the AT condition, as well as a final follow-up surveys 2 weeks after the intervention. The intent of this design is to allow those in the Control condition to also receive any benefits of the intervention.

***The below sections contain additional questions depending on the type of research that you are conducting and is meant to supplement the study overview. Please complete each section, as applicable.***

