## 6. RISK AND BENEFIT ASSESSMENT

6.1 Describe the foreseeable risks associated with your study. Please include discussion of any physical risks and non-physical risks, such as economic, psychological, social, and legal harms.

1. Asking subjects about suicide may cause distress in some patients.
2. Despite the fact that the articles selected by TheMighty decrease the level of suicidal ideation collectively, there may be certain subjects who experience increased SI after reading the assigned articles.
3. If there is mismanagement of data, user names and/or emails may be associated with their activity in the research database, and may become visible to the researchers

6.2 Describe the steps that you will take to minimize risks to your participants (for example, using pseudonyms or a coding system, etc.)

1. In order to address this concern, we will take several measures. First, during the consenting process, we will include language that warns subjects that some of the survey questions may induce distress. Second, we will make sure that subjects can easily exit the study at any time.

It is important to note that research has demonstrated that asking patients about suicide does not appear to increase the level of suicidality (Dazzi et al, 2014). The research team will meet regularly to review data and any adverse effects. [name], licensed clinical psychologist, will oversee these meetings.

2. At the end of each survey, we will provide users with a pop-up that provides information on how to get in touch with a suicide hotline.
3. We will institute an automatic data cleaning process that ensures that all names and emails will be deleted from the database before any researchers have access.

6.3 Are provisions needed for medical and/or psychological support resources (for example, in the event of research-related distress or incidental findings)?

Yes

No

6.4 If applicable, what steps will you take if a participant becomes distressed during your study or reports intent to harm themselves or others?

Should a participant report elevated suicidal ideation, a pop-up screen will be triggered and will provide contact information for a suicide hotline

6.5 Describe any potential direct benefits to participants in the study. If there are no individual benefits, indicate as such.

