Title of study: Digital Narrative Bibliotherapy as a Scalable Intervention for Suicidal Thoughts

Document date: November 20, 2020

Document type: Statistical Analysis Plan

STATISTICAL ANALYSIS PLAN

We used an intent-to-treat design for all analyses, which were performed in RStudio.

Hypothesis 1: We predicted that the narrative bibliotherapy intervention would lead to lower ratings of the desire to die among participants assigned to the Treatment group, relative to those assigned to the Control group.

- **Analysis:** We used a mixed effects model as implemented in the *lme4* package to test whether participants in the Treatment group reported lower desire to die across the 14-day study period. This model included group (Treatment vs. Control) and day of the survey fixed effects. We also controlled for the effects of previous history of suicidal thoughts by including this measure as participant-level fixed effects.

Hypothesis 2: We predicted that the effect of the treatment would persist two weeks after the conclusion of the trial.

- **Analysis:** We used a *t*-test to examine group differences (Treatment vs. Control) in desire to die at the two-week follow up point.

Hypothesis 3: We predicted that participants who completed more days of the trial would report lower desire to die if they were assigned to the Treatment group (i.e. dose response effect).

- **Analysis:** We used a mixed effects model as implemented in the *lme4* package to tested the effect of the number of days of participation on participants' desire to die across the 14-day study period. This model included group and days of participation as participant-level fixed effects.

Hypothesis 4: We predicted that reductions in the desire to die resulting from reading suicide narratives to die would be attributable to increased feelings of optimism and connectedness.

- **Analysis:** We used mediation analysis as implemented in the *lavaan* package to examine the indirect effect of connectedness and optimism on the association between group assignment and desire to die.

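### AT daily ratings are placed around articles and Control ratings are not; the plan neither names the rating used for Hypothesis 1 nor secures AT ratings once reading stops

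*Protocol*

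**What the plan says.** Protocol Section 5.1, Part 1, describes the AT arm: "Participants in the AT condition will be provided at least 1 article per day during the 5-to-14-day initial study period", and "Participants in the AT condition will also receive a survey before and after each article". For the other arm it says "Participants in the Control condition will be sent emails with the same survey as those in the AT condition", without articles. Part 2 carries this structure into the main trial: "The protocol for the actual research trial is nearly identical to the feasibility trial described above". Part 2 also describes the intervention that Control receives later in the same terms, with surveys before and after each article.

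Other passages are looser. The Section 5.1 overview says that AT participants are "assigned to read one story from the mighty per day and to complete a brief online survey". Section 4.2 says that users are "either randomized to the suicide prevention curriculum with daily surveys" or to a control condition with the surveys alone. Section 11.4 awards raffle tokens for completed surveys, not for reading.

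The SAP opens with "We used an intent-to-treat design for all analyses". Its Hypothesis 1 model is a mixed model for desire to die over 14 days, with group, survey day and previous history of suicidal thoughts. It does not choose between pre- and post-article ratings, gives no rule for missing days, and does not say what intent-to-treat means for days without a rating.

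**The concern.** Two features of the measurement differ by arm.

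**Timing relative to reading.** Some AT ratings are taken straight after an article. No Control rating in the comparison period is. If all ratings enter Hypothesis 1, a short-lived lift after reading counts as an effect on the day as a whole.

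**What happens when reading stops.** A post-article rating has no meaning on a day without reading, and no passage provides for a daily rating from an AT participant who has stopped. Disengagement is expected: Section 5.1 thinks it plausible that most participants stop engaging after 5 days. Section 6.1 lists increased suicidal ideation after reading as a risk, so some AT participants could stop for reasons tied to the outcome. If their ratings end at that point, the analysis describes people while they read, not everyone assigned to the curriculum.

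Hypothesis 1 is the first hypothesis in the SAP, and its result could depend on how the survey is delivered as well as on the articles.

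**Working it through.** The documents give no alpha, power, effect size, SD or dropout rate, so there is no planned figure to reproduce. Taken from the documents: 14 days, and 250 per arm (half of the 500 in Part 2; Section 7.1 gives 1000, hence 500 per arm). Everything else below is assumed.

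**1. Number of ratings.** At one article a day, a fully adherent AT participant supplies 2 × 14 = 28 ratings. Control supplies 1 × 14 = 14 if surveyed once a day. Over 5 days the counts are 10 and 5. Half of the AT ratings follow reading.

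**2. Pooling pre and post ratings.** Let the ordinary daily mean be μ in both arms and the post-article mean be μ − d, with the dip gone by the next day. With equal numbers of each, the AT mean is (μ + μ − d)/2 = μ − d/2, and the contrast with Control is −d/2. Post ratings alone give −d; pre ratings alone give 0. For an assumed d of 0.3 SD, pooling contributes 0.15 SD.

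**3. Day-to-day non-response, no true effect.** Model: y = u + e, with var(u) = 0.6 and var(e) = 0.4, so SD is 1 and within-person correlation 0.6. The probability that a rating is returned is 1/(1 + exp(−(0.4 − b·y))), about 60% at y = 0. Groups are compared on person means weighted as in a random-intercept model. The slope b is the log-odds of non-response per SD of that day's rating.

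| b in AT | b in Control | Estimated difference (SD) | Error, 250 per arm |
|---|---|---|---|
| 0.5 | 0.25 | −0.05 | about 9% |
| 0.5 | 0 | −0.09 | about 25% |
| 1.0 | 0.25 | −0.13 | about 45% |
| 0.5 | 0.5 | about 0 | about 4% |
| 0 | 0.5 | +0.09 | – |

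Negative values favour AT. At 500 per arm, error in the second and third rows is about 44% and 74%. Equal slopes give no bias only if response rates are also similar: with Control retention near 85%, equal slopes gave roughly −0.03 to −0.06 SD, with error about 8% to 13%.

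**4. Permanent stopping in AT only, no true effect.** The stopping rate was set so that about half of AT person-days remain, with 250 per arm and a random-intercept model on group and day.

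- Stopping at random: −0.001 SD, error 4%.
- Stopping dependent on earlier observed ratings: −0.006 SD, error 4%.
- Stopping dependent on the current, unobserved rating: −0.07 SD, error 17%.
- The last mechanism in both arms equally: 0.001 SD, error 5%.

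**5. What is estimated if the effect ends with reading.** Assume −0.3 SD on reading days and 0 afterwards, with the same stopping. Ratings on all days give −0.15 to −0.16 SD. Ratings lost in AT when reading stops give −0.30 to −0.37 SD. If Control stops answering equally, the estimate is still −0.30 SD. In this setting the loss of ratings changes the quantity estimated, even when stopping is random.

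**The case against.** A reader might infer four stronger things, and the documents support none of them.

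**That AT outcome collection ends when reading ends.** No passage makes the survey conditional on reading. An article is provided every day regardless, and the pre-article survey can be answered by someone who then does not read. The Section 5.1 overview lists story and survey as two tasks, Section 4.2 speaks of daily surveys, and the raffle rewards surveys. Only the post-article rating plausibly needs the article. Section 6.2 says "we will make sure that subjects can easily exit the study at any time"; it does not say that leaving is the only alternative to reading.

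**That Control keeps answering.** The expected disengagement is not attributed to an arm, and Control ratings also come only from days on which people choose to respond.

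**That Hypothesis 1 is not intent-to-treat.** Groups are compared as assigned. Missing ratings raise a missing-data and estimand question; they do not make this an as-treated analysis. A mixed model on all available ratings showed almost no null bias when stopping was random or depended on observed ratings.

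**That any bias favours Treatment.** AT participants may stop because they feel better, and distressed Control participants may stop answering. Reversing the slopes reversed the sign.

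All of this stands. It does not supply the missing statements: which rating is analysed, whether surveys continue after reading stops, and how missing days are treated. The pooling problem in step 2 needs no dropout at all.

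**Conclusion.** The point holds as a gap in measurement and specification. AT ratings are placed around articles and Control ratings are not, Hypothesis 1 does not name the rating, and nothing secures AT ratings once reading stops. The intent-to-treat statement is not secured; it is not shown to be broken.

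Pooling equal numbers of pre and post ratings adds d/2 to the apparent benefit if the dip fades by the next day. With no true effect, lost ratings matter only if missingness depends on unobserved ratings and differs by arm. Under the values assumed in step 3, that gives about 0.05 to 0.13 SD with error of about 9% to 45% at 250 per arm. It is near 0 when dependence and response rates are equal, and opposite in sign when dependence is stronger in Control. These sizes are illustrations, since the documents give no figure for the dependence.

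Hypothesis 2 is not affected, because its follow-up survey goes to all participants.

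**What to change.** Send both arms the same daily survey email at the same time of day, before and independent of the article link, and keep sending it in AT after a participant stops opening articles. Make this single rating the Hypothesis 1 outcome in both arms. Analyse post-article ratings separately as an immediate effect. Report survey completion by arm and day, and add a delta-adjusted sensitivity analysis in which unreported ratings are shifted by a range of values, separately by arm.

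The SAP is written in the past tense, so the data may already exist. In that case, use the pre-article rating in AT for Hypothesis 1, state whether surveys continued after reading stopped, and apply the completion report and the sensitivity analysis.

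The cost is a platform email setting and some SAP wording; the daily email can take the place of the pre-article survey. Two drawbacks follow. The Hypothesis 1 estimate leaves out the immediate post-article dip and may be smaller. A survey sent apart from the article is also a less tight baseline for the immediate pre/post contrast.
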